11.2 Duration of Response (Groups 1, 2, and 3a)

Duration of Response (DoR) is defined as the time from documentation of tumor response to disease progression or death and will be calculated as:

$$\text{Date of Disease Progression or Death or Censoring} - \text{Date of First PR or CR} + 1$$

By definition, the DoR analysis will only include those patients achieving a CR or PR. Responders who were lost to follow-up or had not progressed or died on study will be censored on the date of their last disease assessment or end-of-study visit (whichever is earliest) and will be calculated as:

$$\text{Date of last response assessment or end-of-study visit (whichever is earliest)} - \text{Date of first study drug dose} + 1$$

Kaplan-Meier methods will be used for the analysis of duration of response. Median (with corresponding 2-sided 95% CI), quartiles (25th and 75th percentiles), minimum, and

maximum duration of response time will be displayed by Phase 2a dose expansion group. A Kaplan- Meier figure of duration of response will be provided as standard for time-to-event endpoints.

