6.18. CT/MRI TUMOR IMAGING & MEASUREMENTS

All measurements should be taken and recorded in metric notation using a ruler, calipers, or a digital measurement tool.

The same method of assessment and the same imaging technique regarding modality, ideally the same scanner, and the use of contrast should be used in a participant throughout the study

to optimize the reproducibility of the assessment of existing and new tumor burden and improve the accuracy of the assessment of response or progression based on imaging.

Assessment should be performed:

- During screening
- Every 6 weeks (-7-day window) from Cycle 1 Day 1 until end of treatment
- At the Safety Follow-Up Visit, if not performed in the previous 6 weeks
- If a patient comes off treatment due to non-RECIST progression, a scan should be obtained during Long Term Follow Up, until radiographic progression is noted.
- Additional scans may be conducted at other time points if deemed clinically appropriate

Scans will be read at the study site. Scans must include chest, abdomen, and pelvis, as well as any other areas of disease, whether or not measurable, present at screening and/or follow-up, including extremities.

Computed Tomography (CT) / Magnetic Resonance Imaging (MRI): Scans are required to document disease status (including chest, abdomen, pelvis, and other regions as clinically indicated). A brain scan is required to exclude brain metastasis if clinically indicated.

Clinical Examination: Imaging-based evaluation is preferred to evaluation by clinical examination unless the lesion(s) being followed cannot be imaged but are assessable by clinical examination. Tumors may also be assessed utilizing visual or palpable lesions on physical examination, including full assessment of all known metastases.

Copies of redacted radiology reports and interventional radiology procedure notes may be obtained for quality control.

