8.4.2.2. Secondary Endpoints

The endpoints below will be assessed by the Investigators. Time to event variables will be estimated using K-M methodology. Medians using the log-log transformation will be computed. Binary variables will be summarized by binomial response rates and their corresponding two-sided 95% exact CI. Quantitative variables will be summarized using the mean, median, minimum, and maximum values, and standard deviation. Categorical variables will be summarized using tables presenting counts and percentages for each category. Further explanation, description, and landmark analyses (e.g., at 12, 24 months) will be provided in the statistical analysis plan finalized before the first database lock.

- ORR is defined as the number and percentage of participants with a BOR of confirmed CR or PR. BOR is defined as the best response designation, recorded between the date of enrollment and the date of the initial objectively documented tumor progression per RECIST v1.1, date of death from any cause, or the date of subsequent therapy, whichever occurs first. For participants without documented progression or subsequent therapy, all available response designations will contribute to the BOR determination.
- DCR is defined as the proportion of participants whose BOR is CR or PR or SD among all randomized participants.

- DoR is defined as the time recorded between the date of enrollment and the date of the initial objectively documented tumor progression per RECIST v1.1, date of death from any cause, or the date of subsequent therapy, whichever occurs first. DoR will be evaluated for responders (i.e., participants with confirmed CR or PR) only.
- Histopathologic Response
- Surgical outcome amputation/limb salvage vs. planned
- Time to local-regional progression or distant progression is defined as the time between the date of enrollment and the date of local recurrence/relapse or distant progression.
- Local-recurrence-free survival is defined as time between the date of enrollment and the date of local recurrence/relapse or death from any cause, whichever occurs first.
- Distant-recurrence free survival is defined as time between the date of enrollment and the date of distant recurrence/relapse or death from any cause, whichever occurs first.
- Disease-free survival is defined as the time between the date of enrollment and the date of recurrence/relapse or death from any cause, whichever occurs first.

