4. SAMPLE SIZE JUSTIFICATION

Groups 1 (Extremity STS) and 3a (Head and Neck)

Sample sizes are guided by Simon 2-stage (optimal) designs based on historical objective responses per indication. Because of the different participant populations (sarcoma and H&N cancers), different criteria are applied to determine the number of participants for each stage and the strength of the efficacy signal that would recommend proceeding to the next stage. Details are described in subsequent sections and in the following Simon 2-Stage Design table:

| | | | Stage 1 responders/ Stage 1 n | | Stage 2 responders/ Stage 2 n | | |
|----------------------------|-------|---------------------------------|----------------------------------|---------------------|----------------------------------|----------------------|-------------------------|
| Group | Power | Historical ORR/Target ORR | Consider Futility | Go to Stage 2 | Consider Futility | Consider Efficacy | Expected Sample Size |
| #1 Extremity Sarcoma | 70% | 20%/35% | ≤3/15 | ≥4/15 | ≤13/46 | ≥14/46 | 25.91 |
| #3 a H&N | 85% | 20%/45% | ≤3/13 | ≥4/13 | ≤8/26 | ≥9/26 | 16.28 |

For sample size calculation and for simplicity of description, recommendations for stopping or progressing to the next stage are based on the number of objective responses observed.

However, since best overall response (BOR) does not necessarily capture the full extent of clinical benefit and since response can be delayed or of short duration, Shasqi will also review other aspects of clinical benefit that may better predict PFS or OS benefit, such as DOR, before making a final determination.

Enrollment will be continued after reaching the indicated number of participants at Stage 1 while the initial efficacy evaluation is ongoing. This will allow additional participants to enroll to account for unexpected trial impact, such as response non-evaluable participants due to early dropout, design parameter change (e.g., historical response rate update), etc.

Although the sample size calculations are based on efficacy considerations, safety will also be continuously assessed and will be considered in the decision to continue or terminate a study treatment population.

Under the optimal Simon 2-stage design criterion:

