11.5 Progression Free Survival (Groups 2 and 3a)

Progression Free Survival (PFS) is defined as the date of first dose of study drug to the date of the initial objectively documented tumor progression per RECIST v1.1 or date of death from any cause whichever occurs first and will be calculated as:

$$\begin{aligned} \text{Date of Disease Progression or Death Date (whichever is earliest)} - \text{Date of First Study} \\ \text{Drug} + 1 \end{aligned}$$

Patients who were lost to follow-up or had not progressed/died on study will be censored on the date of their last disease assessment or end-of-study visit or subsequent therapy (whichever is earliest) and will be calculated as:

Date of last response assessment or end-of-study visit or subsequent therapy (whichever is earliest) – Date of first study drug dose + 1

NOTE: If a patient does not have post-baseline tumor assessment or clinically determined progression and have not died, then the PFS will be censored at Day 1;

Kaplan-Meier methods will be used for the analysis of duration of stable disease. Median (with corresponding 2-sided 95% CI), quartiles (25th and 75th percentiles), minimum, and maximum duration of response time will be displayed. A Kaplan-Meier figure will be provided as standard for time-to-event endpoints.

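### Subsequent therapy drops out of the SAP's duration-of-response rule without being recorded, Group 1 is added with no rule for surgery, and PFS censoring at a switch depends on what happens afterwards

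*SAP*

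**What the plan says.** **DoR, protocol.** Section 8.4.2.2 stops the clock at documented progression, "date of death from any cause, or the date of subsequent therapy, whichever occurs first. DoR will be evaluated for responders".

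**DoR, Phase 2a SAP.** Section 11.2 reads: "Duration of Response (DoR) is defined as the time from documentation of tumor response to disease progression or death". Responders who "had not progressed or died on study will be censored on the date of their last disease assessment or end-of-study visit" take the earlier of those two dates. Subsequent therapy appears in neither the event rule nor the censoring rule. The heading covers Groups 1, 2 and 3a, whereas the endpoint lists (protocol 2.2.2.2, SAP 3.5) give DoR to Groups 2 and 3a only.

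**PFS, Phase 2a SAP.** Section 11.5 (Groups 2 and 3a) counts as the event "the date of the initial objectively documented tumor progression per RECIST v1.1 or date of death from any cause whichever occurs first". Patients lost to follow-up, or who "had not progressed/died on study will be censored on the date of their last disease assessment or end-of-study visit or subsequent therapy", are censored at the earliest of those dates. The protocol's PFS definition does not mention subsequent therapy.

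**Elsewhere in the same SAP.** Best overall response and ORR (11.1), disease control rate (11.4) and exploratory target-lesion DoR (11.16) all still stop at subsequent therapy. Section 16 says that the SAP supersedes the protocol's statistical text, and its table of changes reads N/A.

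**Follow-up.** Under protocol 6.18, for a patient who stops treatment without RECIST progression, "a scan should be obtained during Long Term Follow Up, until radiographic progression is noted". Protocol 3.1.7 follows patients for up to two years after the last cycle.

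**The concern.** Starting non-protocol treatment ends study treatment but not study follow-up (protocol 3.1.5, 3.1.7). Progression after a switch can therefore be recorded. Under SAP 11.2 that later progression date marks the end of a response attributed to SQ3370, although part of the interval was spent on another treatment.

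In Group 1 the plan is definitive surgery after cycle 4, or later if deferred. Once the tumour is removed, time without progression no longer measures drug response. Neither document says whether surgery ends DoR, censors it, or is disregarded.

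In SAP 11.5 the difficulty is the condition placed on censoring. Whether the switch date applies is settled by what the patient does after the switch. Kaplan-Meier needs censoring that does not look ahead, and this rule does.

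DoR has some weight here. SAP section 4 says the sponsor will review other aspects of benefit, "such as DOR, before making a final determination" on moving between stages.

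**Working it through.** The documents give no DoR or PFS figure to reproduce. The check is a worked patient and a simulation on stated assumptions.

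**1. Worked patient (invented).** Enrolment and first dose on day 1, partial response on day 43, new therapy on day 120, progression on day 300.

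| Rule | Calculation | Result |
|---|---|---|
| SAP 11.2 DoR | 300 − 43 + 1 | 258 days, event |
| From response, cut at new therapy | 120 − 43 + 1 | 78 days |
| Protocol 8.4.2.2 DoR (clock starts at enrolment) | 120 − 1 + 1 | 120 days |
| SAP 11.5 PFS | 300 − 1 + 1 | 300 days, event |

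The 78-day row combines the SAP's start with the protocol's end; neither text contains it. It isolates the effect of the cut-off: 258 − 78 = 180 days are added after the switch.

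**2. Same patient, no progression or death, last scan on day 400.** SAP 11.5 censors PFS at day 120, the earliest listed date. SAP 11.2 carries DoR to day 400, which is 400 − 43 + 1 = 358 days from response. The printed censoring formula subtracts the first-dose date instead and gives 400 days. That start-date mismatch is a separate defect in the same section.

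Two patients who both switch on day 120 are thus handled differently: one is an event at day 300, the other is censored at day 120. Censor-at-switch would give day 120 for both. Treatment policy would give an event at day 300 and censoring at day 400.

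**3. Size of the PFS effect.**

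Inputs from the documents:
- Median PFS of 23.3 weeks for doxorubicin (protocol 1.1.1): 23.3 × 7 / 30.4375 = 5.4 months.
- About 8 months of treatment (12 cycles) plus 24 months of follow-up = 32 months.

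Assumptions not in the documents:
- Exponential times.
- 20% or 40% of patients switch before progression, independently of prognosis.
- Post-switch hazard ratio of 1.0 or 0.5.
- An alternative follow-up of 6 to 24 months.

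True 12-month PFS without switching: exp(−ln 2 × 12 / 5.4) = 0.214. Kaplan-Meier 12-month PFS, 200,000 simulated patients:

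| Follow-up | Next-line effect | SAP 11.5, 20% switch | SAP 11.5, 40% switch | Censor-at-switch |
|---|---|---|---|---|
| 6–24 months | none | 19% | 16% | 21% |
| 32 months | none | 21% | 21% | 21% |
| 32 months | HR 0.5 | 24% | 27% | 21% |

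With short follow-up, many switchers are still event-free. Their post-switch event-free time is discarded while others' post-switch events are kept, so the curve falls. With long follow-up nearly every switcher has an event, so little is discarded. An effective next therapy then delays those events and the curve rises.

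**4. Medians at 140 weeks' follow-up.** With no next-line effect, the SAP rule gives 23.2 to 23.4 weeks, matching censor-at-switch. With 40% switching and a hazard ratio of 0.3, it gives 25.8 weeks against 23.3.

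**5. Event or censor.** In the same 140-week simulation, counting new therapy as an event gives a median of 18.7 weeks at 20% switching and 14.0 at 40%, against about 23.3 when it is a censor. The protocol does not say which it intends for DoR, so restoring its wording alone would not settle the analysis.

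**The case against.** **These are descriptive secondary endpoints.** That stands. Neither DoR nor PFS is tested. The Simon rules count responses, and ORR already stops at subsequent therapy. DoR is one of several things the sponsor may review.

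**Following DoR through new therapy is a recognised treatment-policy choice.** It would be legitimate if stated. Here it contradicts the protocol and SAP 11.16, and section 16 does not record it, so it reads as an omission.

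**SAP 11.5 may have meant censoring at subsequent therapy for everyone.** Possibly: it lists that date with an earliest-of rule. But the sentence confines the list to patients lost to follow-up or without progression or death, and a programmer following it would obtain the results above.

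**The SAP is a draft.** Its footer reads version 0.1, and 11.6 promises a further version. That makes correction easy; it does not alter what the text says.

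**A reader might infer that surgery distorts both endpoints.** The documents do not support this. Planned surgery belongs to Group 1, PFS is analysed only in Groups 2 and 3a, and planned major surgery is a general exclusion (protocol 4.1.2). Surgery reaches DoR only, through the Group 1 heading of 11.2.

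**A reader might infer that the PFS rule always biases Kaplan-Meier downward.** It does not. The fall to 19% or 16% needs short follow-up and an ineffective next therapy. At the planned maximum follow-up it almost disappears, and it reverses if next-line treatment works.

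**Conclusion.** The point holds on the text in three parts. SAP 11.2 drops the protocol's subsequent-therapy cut-off without recording it, and is out of line with 11.1, 11.4 and 11.16. SAP 11.2 includes Group 1 against both endpoint lists and without a rule for resection. SAP 11.5, read literally, makes censoring at a switch conditional on the later outcome and matches neither standard estimand.

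The DoR effect can be large for an individual patient (180 days in the example), but the documents do not show how many responders would start new therapy before progressing. For PFS, the simulated 12-month estimate runs from 16% to 27% against about 21%, depending on follow-up, switch rate and next-line effect. All three are assumptions, so these figures show sensitivity and do not forecast a bias. The lack of a fixed sign is itself a reason to correct the rule, because a reader of the results could not adjust for it. It would also be wrong to say that the SAP ignores subsequent therapy throughout; the gap is confined to 11.2 and the scope of 11.5.

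**What to change.** - **SAP 11.2:** restore subsequent anti-cancer therapy as a cut-off for DoR, and state whether that date is an event or a censor.
- **Group 1:** either remove it from 11.2, in line with the endpoint lists, or give it an explicit analysis cut-off at definitive surgery.
- **SAP 11.5:** apply one rule to every patient whatever follows. Censor at the last adequate assessment before subsequent therapy, with the treatment-policy version as a sensitivity analysis.
- **SAP section 16:** record these changes from the protocol.

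The cost is SAP wording and one derived date, the start of first subsequent therapy. Time to first subsequent therapy needs that date anyway, although SAP 11.6 says its data collection is not yet settled, so the date must be confirmed as captured. The price in results is a somewhat shorter reported DoR and fewer PFS events.

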2.2.2.2. Secondary Endpoint

- ORR per RECIST v1.1.
- OS
- Time from enrollment to first subsequent therapy (TFST)
- Plasma concentration and PK parameters for SQP33 prodrug and active Dox following SQ3370 treatment.
- Group 1: Advanced High-risk Soft Tissue Sarcoma of the Extremity
 - Histopathological Response
 - Surgical outcome amputation/limb-salvage vs planned
 - Disease-free survival
 - Local recurrence-free survival [Time Frame: 2 years]
 - Distant recurrence-free survival
 - Symptomatic disease control
- Group 2: Comparison of the RP2D of SQ33 total dose in mg/m² administered every 21 days administered over 3 vs over 5 days
 - Compare safety and tolerability of two infusion schedules of SQP33 (3-day vs 5-day)
 - Pharmacokinetic comparison of the two infusion schedules
 - PFS per RECIST v1.1
 - DoR per RECIST v1.1
 - DCR per RECIST v1.1
- Group 3a: Head & Neck
 - DoR per RECIST v1.1
 - PFS per RECIST v1.1
 - Time to local-regional progression or distant progression per RECIST v1.1
 - Local-regional control per RECIST v1.1
 - DCR per RECIST v1.1

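### SAP 11.2 starts the duration-of-response clock for censored responders at first response in one formula and at first dose in the other; the second adds their time to response

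*SAP*

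**What the plan says.** Section 11.2 of the Phase 2a SAP starts the clock at response: "Duration of Response (DoR) is defined as the time from documentation of tumor response to disease progression or death". Its first formula takes "Date of Disease Progression or Death or Censoring", subtracts "Date of First PR or CR" and adds one day. Because censoring is named as an end date, this formula already covers responders without an event.

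The next paragraph takes responders who were lost to follow-up or had neither progressed nor died. It censors them at the earlier of the last disease assessment and the end-of-study visit, and gives them a second formula whose start date is "Date of first study drug dose". The results feed a Kaplan-Meier analysis with median and confidence interval, quartiles, minimum, maximum and a figure. Section 11.2 of the Phase 1 SAP contains the same pair of formulas.

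There is also a third origin. Protocol 8.4.2.2 and 8.4.2.3 start DoR at enrollment, as does SAP 11.16 for target lesions. SAP section 16 records no change from the protocol.

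Protocol 2.2.2.2 lists "DoR per RECIST v1.1" as a secondary endpoint for Groups 2 and 3a, and SAP 11.2 applies it to Groups 1, 2 and 3a. For the Simon groups, SAP section 4 says the sponsor will also review "other aspects of clinical benefit that may better predict PFS or OS benefit, such as DOR, before making a final determination".

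**The concern.** The two formulas give different durations for the same patient. The SAP states that it supersedes the protocol's statistical text, but that does not settle a conflict inside the SAP. Two programmers working from 11.2 could produce different curves from the same data, each able to point to a line in the plan.

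Following the second formula also distorts in one direction only. Time before response is credited to patients whose response is still ongoing and not to those who have progressed or died. The distortion is greatest when many responders are still censored. That could be the case if DoR is reviewed around Simon Stage 1 in Groups 1 and 3a, although the documents neither fix the timing of that review nor name a Kaplan-Meier DoR output for it.

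**Working it through.** The section gives no numerical DoR figure to reproduce, so the check works from the formulas.

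**Inputs.** The two formulas in SAP 11.2. The scan schedule in Protocol 6.18: "Every 6 weeks (-7-day window) from Cycle 1 Day 1 until end of treatment". The same section allows unscheduled imaging: "Additional scans may be conducted at other time points if deemed clinically appropriate". First dose is Day 1, so the first scheduled scan falls on Days 36 to 43 and the second on Days 78 to 85.

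**Gap for one censored responder.**

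(censor date − first dose + 1) − (censor date − first PR/CR + 1) = first PR/CR − first dose

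The excess is exactly the time to response, whatever the censoring date.

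| First PR | Last scan | From first PR/CR | From first dose | Gap (days) |
|---|---|---|---|---|
| Day 43 | Day 85 | 85 − 43 + 1 = 43 | 85 − 1 + 1 = 85 | 42 |
| Day 36 | Day 85 | 85 − 36 + 1 = 50 | 85 | 35 |
| Day 85 | Day 127 | 127 − 85 + 1 = 43 | 127 | 84 |
| Day 78 | Day 127 | 127 − 78 + 1 = 50 | 127 | 77 |
| Day 22 (unscheduled) | Day 85 | 85 − 22 + 1 = 64 | 85 | 21 |

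**Direction.** Event times are the same under both formulas and censored times only lengthen. The number at risk at each event time is therefore equal or larger, each Kaplan-Meier factor (1 − events / at risk) is equal or larger, and the curve cannot fall.

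**Illustration (assumed outcomes on the 6-week grid).** Five responders, all with PR on Day 43. Three progress on Days 85, 169 and 211; two are ongoing with last scan on Day 127.

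- First formula: times 43, 127, 169, 85+, 85+. S(43) = 4/5 = 0.80; S(127) = 0.80 × 1/2 = 0.40; median 127 days.
- Second formula: times 43, 127, 169, 127+, 127+. S(43) = 0.80; S(127) = 0.80 × 3/4 = 0.60; S(169) = 0; median 169 days.

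This example rests on a tie: the second-formula censored time (127+) coincides with the event at 127 days, so both ongoing patients still count as at risk. With their last scan on Day 126 both formulas give S(127) = 0.40 and a median of 127 days.

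**Range.** To avoid relying on one example, take five responders with PR on Day 43, one to three of them ongoing at Day 127, and the rest progressing on Day 85, 127, 169 or 211. That gives 35 + 20 + 10 = 65 patterns.

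| Ongoing | Patterns | Median higher under second formula |
|---|---|---|
| 1 | 35 | 1 |
| 2 | 20 | 3 |
| 3 | 10 | 4 |
| All | 65 | 8 |

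The median is unchanged in 57 patterns and lower in none. In three of the patterns with three ongoing it goes from 127 days to not reached. The median here is the first time the estimate is at or below 0.5. In two of the 8 patterns the first-formula estimate is exactly 0.5; if the median required an estimate strictly below 0.5, those two would be equal and 6 would remain. Moving the last scan to Day 126 throughout, under the at-or-below convention, gives 12 of 65 higher and again none lower. The patterns are not equally likely, so these counts are not probabilities.

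**The case against.** The strongest reply is that this is a drafting slip that a careful reader would resolve correctly. The definition in words and the first formula both point to first PR or CR. The stray start date fits OS (11.3) and PFS (11.5), which properly begin at first dose, so it looks carried over. That is probably how it arose, but the second formula is the one written specifically for censored responders, so a programmer would have reason to use it. The planned independent quality-control programming cannot settle an ambiguous specification.

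The second reply concerns weight. The Phase 2a primary endpoints are safety, DoR is descriptive, and Stage 1 may have only a handful of responders (4 of 13 or 4 of 15 to continue). The planned swimmer's plot shows response and progression dates directly. The five-responder example depends on a tie, and the median is unchanged in most enumerated patterns. All of this stands, and it limits the consequence. It does not remove the contradiction or change the direction of the error.

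The third reply is about scope. SAP 11.16 agrees with the protocol and is not internally inconsistent, so changing it is a separate step from repairing 11.2. That is fair. The reason to take it in the same revision is that one SAP would otherwise carry two origins for DoR.

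**Conclusion.** The concern holds, and 11.2 should be corrected. As written, it assigns two start dates to the same censored responders, and following the second puts two time origins into one Kaplan-Meier curve.

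The size per patient is certain: the overstatement equals the time to response. The effect on the reported curve or median depends on how many responders are censored and when, which turns on accrual and true DoR; the documents give neither. The five-responder figures are assumed illustrations. With no censoring the formulas agree, and at the final analysis, run once all participants have completed Phase 2a, the effect should be nil or small. Response rates and Simon boundaries are unaffected.

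**What to change.** In Phase 2a SAP 11.2, change the start date in the second formula to the date of first PR or CR. Keep its existing end date, so that every responder is measured from the same origin. Use that origin in 11.16 as well, and list in section 16 the departure from the enrollment-based definitions in Protocol 8.4.2.2 and 8.4.2.3.

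The Phase 1 SAP is already executed, so correct it by amendment or by a documented deviation in the study report.

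Separately, the sponsor should reconcile how subsequent therapy is treated: it ends DoR in Protocol 8.4.2.2, is absent from SAP 11.2, and is a censoring date for PFS in SAP 11.5. No particular rule is proposed here.

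The cost is low. The Phase 2a SAP is a version 0.1 draft with a next version already foreseen, and no new data are needed. The downside is that reported DoR may be shorter.
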